Due to the coding schema involving a conditional coding structure, inter rater reliability involved percent agreement in 3 coding areas: number of geriatric concerns, the category of geriatric domain discussed, and the physician's response quality. *A GA communication composite score will be created by adding all GA-related topics that were discussed for each visit.* For number of geriatric concerns, the percent agreement was calculated using the difference in numbers between each coder and the consensus. An average of all coder agreement was calculated for the category of geriatric domain and physician response quality. If inter-rater agreement percentages fell below 70%, the coding team would meet for additional training. The principal investigator remained involved in the coding process and provided guidance or adjudication when necessary.

Another secondary outcome measure will be patient-reported HRQoL as measured by the FACT and caregiver HRQoL (burden) as measured by the Caregiver Reactions Assessment (CRA). We hypothesize that the mean HRQoL for patients and caregivers at sites randomized to the intervention arm will be higher than for those in the usual care arm at 4-6 weeks following the intervention and that this increase will be both statistically significant and clinically meaningful.^{99,100} We will include GA impairment (at baseline and follow up) to evaluate if these influence patient-reported and caregiver-reported HRQoL differently in the intervention versus the control group. Other secondary outcomes will include whether the intervention impacts how the oncology physician acknowledges and addresses age-related concerns, caregiver burden (as measured by the Caregiver Reaction Survey) and caregiver satisfaction with communication (as measured by the modified HCCQ) at 4-6 weeks. We will follow participants for survival for 12 months after enrollment. We will obtain the date, location of death, and cause of death. If a site becomes aware that a study participant is deceased, they should complete the form which is available on the URCC NCORP website. Otherwise sites will be contacted approximately 1 year after each participant was enrolled to assess survival and asked to complete this form.

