15. STATISTICAL PLAN

15.1. Statistical Considerations

[figure not shown]
This is a cluster-randomized trial with NCORP practice sites being the clusters. Because of the cluster randomized study design, we will apply linear mixed model methodology.¹⁰⁴ The outcome will be the response, and the arm will be the fixed effect. NCORP practice sites will be entered as a random effect independent of residual error. Estimation will be performed using Restricted Maximum Likelihood, and the null hypothesis of zero mean difference between arms will be tested using a F test.¹⁰⁵ The specific NCORP practice site differences will be assessed graphically using Best Linear Unbiased Predictors (BLUP) of the mean response for each NCORP.

All regression analyses will include terms to control for study site and oncologist type. In addition, clinically important socioeconomic variables such as patient gender, age, race/ ethnicity, and cancer variables such as cancer type and treatment status will be used to control for patient-level covariates. In case a key covariate is found to be unbalanced between study arms, it will be included in the model as a potential confounder.

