Analysis for Primary Aim 1. This is a cluster randomized trial with NCORP practice sites being the clusters. Because of the cluster randomized study design, we will apply linear mixed model methodology.¹⁰⁴ The total modified HCCQ scores (HCCQ-age) will be the response, and the arm will be the fixed effect. NCORP practice sites will be entered as a random effect independent of residual error. Estimation will be performed using Restricted Maximum Likelihood, and the null hypothesis of zero mean difference between arms will be tested using the F test.¹⁰⁵ The specific practice site differences will be assessed graphically using Best Linear Unbiased Predictors (BLUP) of the mean response for each site.

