15.4. Other Secondary Analyses

15.4.1. Secondary Aim 2: HRQoL will be assessed with the FACT and Caregiver HRQoL will be assessed with the Caregiver Reactions Assessment (CRA). The analysis will be the same as that used for Primary Aim 1. We will include geriatric assessment impairment (at baseline and follow up) to evaluate if these influence patient-reported HRQoL differently in the intervention versus the control group. We will also compare whether the uptake of geriatric assessment recommendations influences patient reported HRQoL and caregiver burden. Data from the intervention arm will be fit to a linear mixed model with FACT or CRA as the outcome, number and percent of implemented interventions (number implemented/number recommended) as the fixed effect, and NCORP site as a random effect independent of residual error. Analyses will be adjusted for treatment status.

15.4.2. Secondary Aim 3: We will compare the effect of the intervention on caregiver satisfaction (the modified health care climate questionnaire for the caregiver) using the same linear mixed model methodology.

15.4.3. Exploratory Aims: Exploratory aims will evaluate (1) whether the number of discussions about age-related issues during the clinic visit correlates with patient satisfaction, (2) whether the intervention increases the proportion of age-related concerns that are acknowledged and addressed, and (3) if communication about age-related issues influences how patients, caregivers, and oncology physicians make decisions for cancer treatment. An additional exploratory aim will examine the impact of the intervention on survival.

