## 4 Statistical Analysis

### 4.1 Statistical Considerations

This is a cluster-randomized trial with NCORP practice sites being the clusters. Because of the cluster randomized study design, we will apply linear mixed model methodology. The outcome will be the response, and the arm will be the fixed effect. NCORP practice sites will be entered as a random effect independent of residual error. Estimation will be performed using Restricted Maximum Likelihood, and the null hypothesis of zero mean difference between arms will be tested using a F test. The specific NCORP practice site differences will be assessed graphically using Best Linear Unbiased Predictors (BLUP) of the mean response for each NCORP.

All regression analyses will include terms to control for study site and oncologist type. In addition, clinically important socioeconomic variables such as patient gender, age, race/ ethnicity, and cancer variables such as cancer type and treatment status will be used to control for patient-level covariates. In case a key covariate is found to be unbalanced between study arms, it will be included in the model as a potential confounder.

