#### **4.5 Missing Data**

Every effort will be made to encourage and facilitate participants' completion of questionnaires, but because of dropout, missing data will occur. We will evaluate the patterns of missing data and associations of missingness with other available variables. Under the missing at random (MAR) assumption, the parameter estimates from the mixed model analyses will be unbiased. If the data are suspected to be missing not at random (MNAR), a sensitivity analysis using pattern-mixture models will be run to determine the impact on the results.

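### The quality-of-life model omits the collected baseline score, so the claim of unbiasedness under MAR at 4-6 weeks covers only missingness explained by variables in the model

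*Protocol*

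**What the plan says.** Protocol 15.4.1 specifies the Secondary Aim 2 analysis by reference: "The analysis will be the same as that used for Primary Aim 1". The Primary Aim 1 model, under Protocol 15.2, is: "The total modified HCCQ scores (HCCQ-age) will be the response, and the arm will be the fixed effect", and "NCORP practice sites will be entered as a random effect independent of residual error".

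Other terms are added elsewhere. Protocol 15.1 says "All regression analyses will include terms to control for study site and oncologist type". Protocol 15.1 and SAP 4.1 add gender, age and race/ethnicity, and in the SAP's words "cancer variables such as cancer type and treatment status will be used to control for patient-level covariates". A key covariate found unbalanced between arms is also to be included. For this aim Protocol 15.4.1 adds: "We will include geriatric assessment impairment (at baseline and follow up) to evaluate if these influence patient-reported HRQoL differently".

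The measures tables (Protocol Appendix X-1, SAP 3.7) show FACT at the baseline visit and Caregiver Reaction at screening. Both are repeated at 4-6 weeks, 3 months and 6 months. Neither document lists the baseline score of either instrument as a covariate.

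Protocol 7.2 gives the time point: mean quality of life in the intervention arm "will be higher than for those in the usual care arm at 4-6 weeks following the intervention". SAP 4.4.1 gives no time point and does not carry over the sentence linking this aim to the primary model.

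On missing data, SAP 4.5 (like Protocol 15.5) says: "Under the missing at random (MAR) assumption, the parameter estimates from the mixed model analyses will be unbiased". SAP 3.5.2 says missingness will be assumed non-random, because sicker patients are less likely to return surveys.

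**The concern.** A mixed model is robust to MAR dropout because of what it conditions on. If a patient's other measurements are in the likelihood, missingness may depend on them. A model for one visit, with a site effect and no earlier score from the same patient, has nothing of that kind. A patient who misses 4-6 weeks is dropped, and the fit is a complete-case analysis. It is unbiased if missingness depends only on arm, site and the covariates in the model. MAR given baseline quality of life, which the usual meaning of MAR would include, is not enough.

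At stake is a secondary comparison in a population with advanced cancer. SAP 3.4.1 reports 48 withdrawn, 61 expired and 4 lost to follow-up among 413 enrolled, which is 113/413 = 27% over the study so far. If responders differ in baseline quality of life between arms, the estimated effect carries that difference.

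**Working it through.** **The plan's own figures.** No power or precision figure is given for Secondary Aim 2. The primary-aim figures reproduce: (t₀.₉₇₅,₁₄ + t₀.₈₀,₁₄) × SD × √[2(1 + (m − 1)ICC)/(km)] with k = 8, m = 31, SD = 2.1 gives 0.648, 1.296 and 2.294 for ICC 0.01, 0.14 and 0.51, against the stated 0.6, 1.3 and 2.3. They do not bear on this point.

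**Assumptions.** The documents give no FACT SD, no baseline-to-follow-up correlation r and no 4-6 week completion rate. I take r = 0.5 to 0.7, work in SD units, and assume about 30% missing. The nearest document figures are 70% completion at 3 months and 64% at 6 months, from another study cited in Protocol 7.3.2.

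**Formula.** Let B be the standardised baseline score. With no true effect, the expected mean among responders in an arm is r × E[B | observed]. The bias without baseline in the model is therefore

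bias = r × (E[B | observed, intervention] − E[B | observed, control]).

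The probability of responding is logistic in B, with slope 1 where dependence is present. E[B | observed] comes from numerical integration. Figures in brackets are from simulating the REML model with arm and a random site intercept (500 patients, 68 unequal sites, site ICC 0.05, 1,500 runs, simulation error 0.003).

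| Dropout mechanism | Control: completion, E[B] | Intervention: completion, E[B] | Bias, r = 0.5 | Bias, r = 0.7 |
|---|---|---|---|---|
| Same in both arms | 67%, 0.277 | 67%, 0.277 | 0 (0.000) | 0 (0.003) |
| Completion rate differs | 58%, 0.346 | 76%, 0.204 | 0.5 × −0.142 = −0.071 (−0.066) | 0.7 × −0.142 = −0.099 (−0.102) |
| Depends on baseline in control only | 67%, 0.277 | 70%, 0 | 0.5 × −0.277 = −0.139 (−0.136) | 0.7 × −0.277 = −0.194 (−0.191) |

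The sign follows from which arm loses more of its sicker patients and could be reversed.

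**Milder cases.** With completion of 63% and 71%, E[B] is 0.312 and 0.242, and the bias is 0.5 to 0.7 × −0.070 = −0.035 to −0.049. With less missing data (87% and 90% completion, dependence in control only), E[B] is 0.119 and 0, and the bias is −0.060 to −0.083.

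**With baseline in the model.** In all six simulated cases the bias lies between −0.002 and 0.005.

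**With a weak covariate instead.** A covariate correlated 0.3 with baseline leaves −0.061 to −0.175 in the four cases where the mechanism differs.

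**Precision.** Adjusting for baseline removes a share r² of patient-level variance: 0.5² = 25% to 0.7² = 49%.

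**The case against.** **The model is richer than arm and site.** A reader of Protocol 15.4.1 alone might infer that it contains nothing else. That is wrong: Protocol 15.1 and SAP 4.1 add oncologist type, demographics, cancer type and treatment status, and 15.4.1 adds GA impairment. Some of these will predict dropout, and baseline GA impairment probably tracks baseline quality of life. This reduces the problem but does not remove it, as the weak-covariate result shows. Follow-up GA impairment is collected at the same visits as the outcome, so it is unlikely to help for a patient who misses the visit. The imbalance rule could bring in baseline FACT, but only conditionally and only if it counts as a key covariate, a term left undefined.

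**Bias needs a mechanism that differs by arm.** This stands. With the same mechanism in both arms, each arm mean shifts by 0.14 to 0.20 SD but the difference does not. The documents report no dropout by arm. A difference is possible because sites know their allocation and Arm 1 patients receive the summary, but that is not evidence of one.

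**Missing data get more than one sentence.** Both documents plan to examine missingness patterns, and to run a pattern-mixture analysis (or, in the protocol, a selection model) if MNAR is suspected. That is useful, but it does not put the baseline score into the main analysis.

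**Pooled visits.** A reader might also infer that repeated scores will be treated as independent, making the arm standard error too small. No section plans to pool visits, and Protocol 7.2 names one time point. Even if visits were pooled, arm is assigned by site, so the site random effect absorbs the omitted patient correlation. In simulation (16 or 68 sites, within-patient correlation 0.5 or 0.7, site ICC 0 to 0.14), model SE over empirical SD was 0.995 to 1.04, and type I error was 3.8% to 5.3%. Only patient-level terms, such as arm by GA impairment, would have standard errors that are too small.

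**Conclusion.** The point holds in a limited form. The Secondary Aim 2 model leaves out a baseline score that the trial collects, and the MAR statement is broader than a single-visit model can support. Under the assumed correlation of 0.5-0.7 and about 30% missing, bias in the arm difference is about zero if dropout works alike in both arms. It is roughly 0.05 to 0.19 SD if it does not, and smaller if the arms differ only mildly. At an assumed FACT SD of 15, that range is 0.05 × 15 = 0.75 to 0.19 × 15 = 2.85 points. Including baseline brings it to about zero under missingness driven by baseline.

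The documents do not support saying that the arm comparison is biased as planned, that the model has only arm and site, or that its false-positive rate is inflated. The separate gain in precision, 25-49% of patient-level variance, does not depend on any dropout assumption. The primary aim is not affected.

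**What to change.** - **SAP 4.4.1:** state that the arm contrast for FACT and the Caregiver Reaction Assessment is at 4-6 weeks, as in Protocol 7.2, and add the baseline score of the same instrument as a fixed covariate.
- **Optional:** fit a repeated-measures model with all three follow-up visits, visit, arm-by-visit, baseline score, site random effect and within-patient covariance. The test stays at 4-6 weeks, with 3 and 6 months supportive.
- **SAP 4.5 and Protocol 15.5:** limit the MAR sentence to missingness that depends on variables in the model.
- **SAP 4.4.2:** caregiver HCCQ-age is collected only at follow-up, so the baseline covariate does not apply there.

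One check when using baseline FACT: Protocol 11.3.1b lets baseline surveys be finished later on the day of the baseline visit, so some scores may follow the consultation. A sensitivity analysis without those patients would be sensible if the order was recorded.

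The cost is SAP wording and slightly more modelling, fixed before the arm comparison is run. No new data are required.

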15.5. Missing Data

Every effort will be made to encourage and facilitate participants' completion of questionnaires, but because of dropout, missing data will occur. We will evaluate the patterns of missing data and associations of missingness with other available variables. Under the missing at random (MAR) assumption, the parameter estimates from the mixed model analyses will be unbiased. If the data are suspected to be missing not at random (MNAR), a sensitivity analysis using selection and/or pattern-mixture models will be run to determine the impact on the results.¹⁰⁶ If the estimates are similar to the ones obtained from the simpler analysis of only complete cases, we will report the complete-case analysis results.

16. DATA MANAGEMENT AND QUALITY ASSURANCE

16.1. Training Procedures

A special training session was held at the 2013 annual URCC NCORP Research Base meeting. This training included a detailed review of the study rationale, design, and research administration procedures. Training sessions will be held with the staff from each site via teleconference and at the annual meetings. These sessions and the corresponding procedures manuals review the following: 1) informed consent; 2) completing the assessments using Teleforms; 3) completing the functional and objective measures; 4) data collection via chart extraction; 5) completing the web-based intervention using mycarg.org (for intervention arm); 6) transfer of the data to the URCC NCORP Research Base; 7) formulating the research chart; and 8) a discussion of interviewing techniques so that the research team will standardize their approaches in order to elicit consistent data from subjects. There will be a protocol update every year at the annual Research Base meeting. All assessments, data collection forms, and manuals will be readily available on the NCORP Research Base website.

16.2. Data Management

The same protocols and procedures for data quality and control that we use for all URCC NCORP Research Base protocols (which accrued over 1,000 patients in the previous year) will be used for this study. Once the patient consents to the protocol, he/she will be assigned a unique identifier by the Research Base, which will be used to link all patient data. Oncology physician and patient assessments will be captured using scannable Teleforms. The CRA and/or Research Nurse at each site will ensure that data are complete prior to submission. At the Research Base, data are scanned into an electronic password-secured Access database which is backed up every 24 hours. At the Research Base, staff to ensure that all data are collected in order to minimize missing data by employing multi-step verification procedures and querying originating sites for missing or ambiguous data. Audio-recordings will be submitted to the Research Base within 24 hours and stored securely as source documentations in accordance with HIPAA compliance. Audio-recordings will be transcribed and de-identified by persons who are not direct members of the study staff.

16.3. REDCap

Data are also collected and managed by the URCC Research Base using REDCap electronic data capture tools hosted at the University of Rochester Medical Center (URMC). We will evaluate records, clinical characteristics, and outcomes and we will utilize REDCap to collect and manage this information. Further, we will link this information to the encrypted ACCESS database (which contains the survey information) with a unique identifier.

16.3.1. The University of Rochester Medical Center provides the following information on the **REDCap program**: “Vanderbilt University, in collaboration with a consortium of institutional partners, has developed a software toolset and workflow methodology for electronic collection and management of research and clinical trial data, called REDCap (Research Electronic Data Capture). The REDCap system is a secure, web-based application that is flexible enough to be used for a variety of types of research. It provides an intuitive interface for users to enter data and real time validation rules (with automated data type and range checks) at the time of data entry. REDCap offers easy data manipulation with audit trails and functionality for reporting, monitoring and querying patient records, as well as an automated export mechanism to common statistical packages (SPSS, SAS, Stata, R/S-Plus). Through the REDCap Consortium, Vanderbilt has disseminated REDCap for use around the world. Currently, over 240 academic and non-profit consortium partners on six continents with over 26,000 research end-users use REDCap”

16.3.2. *According to the University of Rochester Clinical and Translational Science Institute (CTSI), REDCap is supported with the following means.* “The *CTSI Informatics Core*, a unit of the *SMD Academic Information Technology (AIT) Group*, will serve as a central facilitator for data processing and management. REDCap data collection projects rely on a thorough study-specific data dictionary defined in an iterative self-documenting process by all members of the research team, with planning assistance from the *AIT-CTSI Informatics Core*. The iterative development and testing process results in a well-planned data collection strategy for individual studies.”

17. DATA COLLECTION AND MEASURES

For a detailed description of the measures that will be collected, refer to **Appendix X-1: Measures**.

18. SUBJECT CONSENT AND PEER JUDGMENT

All investigational, FDA, state, federal and institutional regulations concerning informed consent and peer judgment will be fulfilled.

19. RECORD AND DATA RETENTION

Clinical research records are source documents and records, in any form (including, but not limited to, written, electronic, magnetic, and optical records, in addition, scans (x-rays and electrocardiograms) that describe or record the methods, conduct, and/or results of a trial, and the actions taken. Unlike pharmaceutical-sponsored research, under the Terms of the NIH Award, the awardee institution retains ownership of the clinical research records that were conducted with NIH support. Records may be preserved in hardcopy, electronic or other media form since there is no regulatory requirement that clinical research records be retained in a certain type of format. However, investigators should check with their institution for institutional policies and procedures pertaining to record retention. All records relating to research that is conducted must be retained for at least five years after completion of the research. The three-year time period begins when the individual institution's engagement in the human subjects research activity ends. Human subject research activities are considered completed once all research-related interventions and interactions with human subjects have been completed, all data collection and analysis of identifiable private information described in the IRB-approved research plan have been finished and primary analysis of either identifiable private or de-identified information is completed.

